5.4. Screen Failures

Screen failures are defined as participants who consent to participate in the clinical study but are not subsequently enrolled in the study. Screen failure data are collected and remain as source and are not reported on the CRF.

Individuals who do not meet the criteria for participation in this study (screen failure) may be rescreened.

6. STUDY INTERVENTION(S) AND CONCOMITANT THERAPY

Study intervention is defined as any investigational intervention(s), marketed product(s), placebo, medical device(s), or study procedure(s) intended to be administered to a study participant according to the study protocol.

For the purposes of this protocol, study intervention refers to PF-07265803.

6.1. Study Intervention(s) Administered

One batch of GMP [¹⁴C]PF-07265803 API will be prepared with the oral dose being fully radio-diluted (100 µCi / 400 mg (~0.25 µCi/mg)) to the overall specific activity requirements for oral dosing. A bulk bottle of this will be shipped to the CRU from the radiochemical vendor.

[¹⁴C]PF-07265803 components for oral administration will be supplied by Pfizer as bulk API and, where necessary, bulk excipients for the manufacture of the oral formulation. The final product composition and presentation will be detailed in a separate Extemporaneous Dispensing Record (EDR) for the [¹⁴C] labeled oral formulation.

6.1.1. Administration

Following an overnight fast of at least 10 hours, participants will receive study intervention at approximately 0800 hours (plus or minus 2 hours). Investigator site personnel will administer study intervention according to the EDR.

In order to standardize the conditions on PK sampling days, all participants will be required to refrain from lying down (except when required for BP, pulse rate, and ECG measurements), eating, and drinking beverages other than water during the first 4 hours after dosing.

6.2. Preparation, Handling, Storage, and Accountability

1. The investigator or designee must confirm appropriate temperature conditions have been maintained during transit for all study interventions received and any discrepancies are reported and resolved before use of the study intervention.

2. Only participants enrolled in the study may receive study intervention and only authorized site staff may supply or administer study intervention. All study interventions must be stored in a secure, environmentally controlled, and monitored (manual or automated recording) area in accordance with the labeled storage conditions with access limited to the investigator and authorized site staff. At a minimum, daily minimum and maximum temperatures for all site storage locations must be documented and available upon request. Data for nonworking days must indicate the minimum and maximum temperatures since previously documented for all site storage locations upon return to business.
3. Any excursions from the study intervention label storage conditions should be reported to Pfizer upon discovery along with any actions taken. The site should actively pursue options for returning the study intervention to the storage conditions described in the labeling, as soon as possible. Once an excursion is identified, the study intervention must be quarantined and not used until Pfizer provides permission to use the study intervention. Specific details regarding the definition of an excursion and information the site should report for each excursion will be provided to the site in the EDR/Roles and Responsibilities Matrix.
4. Any storage conditions stated in the SRSD will be superseded by the storage conditions stated on the label.
5. Study interventions should be stored in their original containers.
6. See the EDR and the IP manual for storage conditions of the study intervention once reconstituted and/or diluted.
7. The investigator, institution, or the head of the medical institution (where applicable) is responsible for study intervention accountability, reconciliation, and record maintenance (ie, receipt, reconciliation, and final disposition records), such as the IPAL or sponsor-approved equivalent. All study interventions will be accounted for using a study intervention accountability form/record as detailed in the IP manual.
8. Further guidance and information for the final disposition of unused study interventions are provided in the IP Manual. All destruction must be adequately documented. If destruction is authorized to take place at the investigator site, the investigator must ensure that the materials are destroyed in compliance with applicable environmental regulations, institutional policy, and any special instructions provided by Pfizer as detailed in the IP manual.

Upon identification of a product complaint, notify the sponsor within 1 business day of discovery as described in the IP Manual.

6.2.1. Preparation and Dispensing

Within this protocol, preparation refers to the investigator site activities performed to make the study intervention ready for administration or dispensing to the participant by qualified

staff. Dispensing is defined as the provision of study intervention, concomitant treatments, and accompanying information by qualified staff member(s) to a healthcare provider, participant in accordance with this protocol and the IP Manual. Local health authority regulations or investigator site guidelines may use alternative terms for these activities.

PF-07265803 oral dosing formulation will be prepared in the CRU by 2 operators, 1 of whom is a pharmacist. Details of dose preparation will be given in a separate EDR located in the IP Manual. Prepared doses will be provided in unit dose containers and labeled in accordance with Pfizer regulations and the investigator site's labeling requirements.

6.3. Measures to Minimize Bias: Randomization and Blinding

This study is an open-label study.

6.3.1. Allocation to Study Intervention

The investigator's knowledge of the treatment should not influence the decision to enroll a particular participant or affect the order in which participants are enrolled.

6.4. Study Intervention Compliance

When the individual dose for a participant is prepared from a bulk supply, the preparation of the dose will be confirmed by a second qualified member of the study site staff.

When participants are dosed at the site, they will receive study intervention directly from the investigator or designee, under medical supervision. The date and time of each dose administered in the clinic will be recorded in the source documents and recorded in the CRF. The dose of study intervention and study participant identification will be confirmed at the time of dosing by a member of the study site staff other than the person administering the study intervention. Study site personnel will examine each participant's mouth to ensure that the study intervention was ingested.

6.5. Dose Modification

Not applicable.

6.6. Continued Access to Study Intervention After the End of the Study

No intervention will be provided to study participants at the end of their study participation.

6.7. Treatment of Overdose

For this study, any dose of PF-07265803 greater than 400 mg (+/- 10% based on the preparation of the final oral dosing formulation) within a 24-hour time period [± 2 hours] will be considered an overdose.

There is no specific treatment for an overdose.

In the event of an overdose, the investigator/treating physician should:

1. Contact the medical monitor within 24 hours.
2. Closely monitor the participant for any AEs/SAEs and laboratory abnormalities for at least 5 half-lives or 28 calendar days after the overdose of PF-07265803 (whichever is longer).
3. Document the quantity of the excess dose as well as the duration of the overdose in the CRF.
4. Overdose is reportable to Pfizer Safety **only when associated with an SAE**.
5. Obtain a blood sample for PK analysis within as soon as possible from the date of the last dose of study intervention if requested by the medical monitor (determined on a case-by-case basis).

6.8. Concomitant Therapy

Use of prescription or nonprescription drugs and dietary and herbal supplements are prohibited within 7 days or 5 half-lives (whichever is longer) prior to the first dose of study intervention with the exception of moderate/potent CYP3A inducers which are prohibited within 14 days plus 5 half-lives prior to the first dose of study intervention. Limited use of nonprescription medications that are not believed to affect participant safety or the overall results of the study may be permitted on a case-by-case basis (e.g. to treat an AE) following approval by the sponsor.

If an individual participant has not experienced a bowel movement within a 36 – 48 hour window following dose administration, fluid intake should be increased and administration of a mild laxative (e.g., prune juice, milk of magnesia or a mild stool softener) should be implemented, with the goal to facilitate at least one daily bowel movement. A mild laxative may also be used prior to dosing to assist with collection of a pre-dose fecal sample, irrespective of the time of last bowel movement. Acetaminophen/paracetamol may be used at doses of ≤ 1 g/day.

Treatments taken within 28 days before the first dose of study intervention will be documented as a prior treatment. Treatments taken after the first dose of study intervention will be documented as concomitant treatments.

6.8.1. Rescue Medicine

There is no rescue therapy to reverse the AEs observed with PF-07265803; standard medical supportive care must be provided to manage the AEs.

7. DISCONTINUATION OF STUDY INTERVENTION AND PARTICIPANT DISCONTINUATION/WITHDRAWAL

7.1. Discontinuation of Study Intervention

Since this is a single-dose study, this section is not applicable.

7.1.1. Potential Cases of Acute Kidney Injury

Abnormal values in SCr concurrent with presence or absence of increase in BUN that meet the criteria below, in the absence of other causes of kidney injury, are considered potential cases of acute kidney injury and should be considered important medical events.

An increase of ≥ 0.3 mg/dL (or ≥ 26.5 μ mol/L) in SCr level relative to the participant's own baseline measurement should trigger another assessment of SCr as soon as practically feasible, preferably within 48 hours from awareness.

If the second assessment (after the first observations of ≥ 0.3 mg/dL [or ≥ 26.5 μ mol/L] in SCr relative to the participant's own baseline measurement) is ≥ 0.4 mg/dL (or ≥ 35.4 μ mol/L), the participant should be discontinued from the study and adequate, immediate, supportive measures taken to correct apparent acute kidney injury.

Participants should return to the investigator site and be evaluated as soon as possible, preferably within 48 hours from awareness of the second assessment confirming abnormal SCr result. This evaluation should include laboratory tests, detailed history, and physical assessment. In addition to repeating SCr, laboratory tests should include serum BUN, serum creatine kinase, and serum electrolytes (including at a minimum potassium, sodium, phosphate/phosphorus, and calcium), in addition to urinary dipstick, urine microscopic examination, and urinary indices. All cases confirmed on repeat testing as meeting the laboratory criteria for acute kidney injury, with no other cause(s) of laboratory abnormalities identified, should be considered potential cases of drug-induced kidney injury irrespective of availability of all the results of the investigations performed to determine etiology of the abnormal SCr. If ≥ 2 healthy participants in a given period are noted to have 2 consecutive SCr results of ≥ 0.3 mg/dL (or ≥ 26.5 μ mol/L), an assessment of whether the finding may be considered an adverse drug reaction should be undertaken.

7.2. Participant Discontinuation/Withdrawal From the Study

A participant may withdraw from the study at any time at his/her own request. Reasons for discontinuation from the study include the following:

- Refused further study procedures;
- Lost to follow-up;
- Death;
- Study terminated by sponsor;

At the time of discontinuing from the study, if possible, an early discontinuation visit should be conducted. See the [SoA](#) for assessments to be collected at the time of study discontinuation and follow-up and for any further evaluations that need to be completed.

The early discontinuation visit applies only to participants who are enrolled/randomized and then are prematurely withdrawn from the study. Participants should be questioned regarding their reason for withdrawal.

If a participant withdraws from the study, he may request destruction of any remaining samples taken and not tested, and the investigator must document any such requests in the site study records and notify the sponsor accordingly.

If the participant withdraws from the study and also withdraws consent (see Section 7.2.1) for disclosure of future information, no further evaluations should be performed and no additional data should be collected. The sponsor may retain and continue to use any data collected before such withdrawal of consent.

7.2.1. Withdrawal of Consent

Participants who request to discontinue receipt of study intervention will remain in the study and must continue to be followed for protocol-specified follow-up procedures. The only exception to this is when a participant specifically withdraws consent for any further contact with him or her or persons previously authorized by the participant to provide this information. Participants should notify the investigator in writing of the decision to withdraw consent from future follow-up, whenever possible. The withdrawal of consent should be explained in detail in the medical records by the investigator, as to whether the withdrawal is only from further receipt of study intervention or also from study procedures and/or posttreatment study follow-up, and entered on the appropriate CRF page. In the event that vital status (whether the participant is alive or dead) is being measured, publicly available information should be used to determine vital status only as appropriately directed in accordance with local law.

7.3. Lost to Follow up

A participant will be considered lost to follow-up if he or she repeatedly fails to return for scheduled visits and is unable to be contacted by the study site.

The following actions must be taken if a participant fails to attend a required study visit:

- The site must attempt to contact the participant and reschedule the missed visit as soon as possible. Counsel the participant on the importance of maintaining the assigned visit schedule and ascertain whether the participant wishes to and/or should continue in the study;
- Before a participant is deemed lost to follow-up, the investigator or designee must make every effort to regain contact with the participant (where possible, 3 telephone calls and, if necessary, a certified letter to the participant's last known mailing

address or local equivalent methods). These contact attempts should be documented in the participant's medical record;

- Should the participant continue to be unreachable, he/she will be considered to have withdrawn from the study.

8. STUDY ASSESSMENTS AND PROCEDURES

The investigator (or an appropriate delegate at the investigator site) must obtain a signed and dated ICD before performing any study-specific procedures.

Study procedures and their timing are summarized in the [SoA](#). Protocol waivers or exemptions are not allowed.

Safety issues should be discussed with the sponsor immediately upon occurrence or awareness to determine whether the participant should continue or discontinue study intervention.

Adherence to the study design requirements, including those specified in the [SoA](#), is essential and required for study conduct.

All screening evaluations must be completed and reviewed to confirm that potential participants meet all eligibility criteria. The investigator will maintain a screening log to record details of all participants screened and to confirm eligibility or record reasons for screening failure, as applicable.

Healthy participants will be screened up to 28 days prior to dosing to determine eligibility. If the time between screening and dosing exceeds 28 days as a result of unexpected delays (eg, delayed drug shipment), then participants do not require rescreening if the laboratory results obtained prior to first dose administration meet eligibility criteria.

A participant who qualified for this protocol but did not enroll from an earlier cohort/group may be used in a subsequent cohort/group without rescreening, provided laboratory results obtained prior to the first dose administration meet eligibility criteria for this study. In addition, other clinical assessments or specimen collections, eg, banked biospecimens, may be used without repeat collection, as appropriate.

Every effort should be made to ensure that protocol-required tests and procedures are completed as described. However, it is anticipated that from time to time there may be circumstances outside the control of the investigator that may make it unfeasible to perform the test. In these cases, the investigator must take all steps necessary to ensure the safety and well-being of the participant. When a protocol-required test cannot be performed, the investigator will document the reason for the missed test and any corrective and preventive actions that he or she has taken to ensure that required processes are adhered to as soon as possible. The study team must be informed of these incidents in a timely manner.

For samples being collected and shipped, detailed collection, processing, storage, and shipment instructions and contact information will be provided to the investigator site prior to initiation of the study.

The total blood sampling volume for individual participants in this study is approximately 312 mL. The actual collection times of blood sampling may change. Additional blood samples may be taken for safety assessments at times specified by Pfizer, provided the total volume taken during the study does not exceed 500 mL during any period of 56 consecutive days.

Table 1. Blood Sampling Volume

Sample Type	Sample Volume (mL)	Number of Sampling Times		Total Volume (mL)
		Screening	Study Period	
Clinical Laboratory Tests	16	1		16
Clinical Laboratory Tests	8		2	16
PK of PF-07265803	4		15	60
Total radioactivity (post-dose)	4		14	56
Total radioactivity (pre-dose)	10		1	10
Metabolite ID	10		15	150
Banked Biospecimen for DNA – Prep D1	4		1	4
TOTAL				312

To prepare for study participation, participants will be instructed on the information in the Lifestyle Considerations and Concomitant Therapy sections of the protocol.

8.1. Efficacy Assessments

There are no efficacy assessments included in this protocol.

8.2. Safety Assessments

Planned time points for all safety assessments are provided in the [SoA](#). Unscheduled clinical laboratory measurements may be obtained at any time during the study to assess any perceived safety issues.

8.2.1. Physical Examinations

A complete physical examination will include, at a minimum, head, ears, eyes, nose, mouth, skin, heart and lung examinations, lymph nodes, and gastrointestinal, musculoskeletal, and neurological systems.

A brief physical examination will include, at a minimum, assessments of general appearance, the respiratory and cardiovascular systems, and participant-reported symptoms.

Physical examinations may be conducted by a physician, trained physician's assistant, or nurse practitioner as acceptable according to local regulation.

Height and weight will also be measured and recorded as per the [SoA](#). For measuring weight, a scale with appropriate range and resolution is used and must be placed on a stable, flat surface. Participants must remove shoes, bulky layers of clothing, and jackets so that only light clothing remains. They must also remove the contents of their pockets and remain still during measurement of weight.

Physical examination findings collected during the study will be considered source data and will not be required to be reported, unless otherwise noted. Any untoward physical examination findings that are identified during the active collection period and meet the definition of an AE or SAE ([Appendix 3](#)) must be reported according to the processes in [Sections 8.3.1](#) to [8.3.3](#).

8.2.2. Vital Signs

Supine BP will be measured with the participant's arm supported at the level of the heart, and recorded to the nearest mm Hg after approximately 5 minutes of rest. The same arm (preferably the dominant arm) will be used throughout the study. Participants should be instructed not to speak during measurements.

The same properly sized and calibrated BP cuff will be used to measure BP each time. The use of an automated device for measuring BP and pulse rate is acceptable; however, when done manually, pulse rate will be measured in the brachial/radial artery for at least 30 seconds. When the timing of these measurements coincides with a blood collection, BP and pulse rate should be obtained prior to the nominal time of the blood collection.

Additional collection times, or changes to collection times, of BP and pulse rate will be permitted, as necessary, to ensure appropriate collection of safety data.

8.2.3. Electrocardiograms

Standard 12-lead ECGs utilizing limb leads should be collected at times specified in the [SoA](#) section of this protocol using an ECG machine that automatically calculates the heart rate and measures PR, QT, and QTc intervals and QRS complex. Alternative lead placement methodology using torso leads (eg, Mason-Likar) should not be used given the potential risk of discrepancies with ECGs acquired using standard limb lead placement. All scheduled ECGs should be performed after the participant has rested quietly for at least 5 minutes in a supine position.

To ensure safety of the participants, a qualified individual at the investigator site will make comparisons to baseline measurements. Additional ECG monitoring will occur if a) a postdose QTcF interval is increased by ≥ 60 msec from the baseline (predose) **and** is > 450 msec; or b) an absolute QT value is ≥ 500 msec for any scheduled ECG. If either of these conditions occurs, then 2 additional ECGs will be collected approximately 2 to 4 minutes apart to confirm the original measurement. If the QTc values from these repeated ECGs remain above the threshold value, then a single ECG must be repeated at least hourly until QTc values from 2 successive ECGs fall below the threshold value that triggered the repeat measurement.

If either of these conditions occurs, then a single ECG measurement must be repeated at least hourly until QTc values from 2 successive ECGs fall below the threshold value that triggered the repeat measurement.

If a) a postdose QTcF interval remains ≥ 60 msec from the baseline **and** is > 450 msec; or b) an absolute QT value is ≥ 500 msec for any scheduled ECG for greater than 4 hours (or sooner, at the discretion of the investigator); or c) QTcF intervals get progressively longer, the participant should undergo continuous ECG monitoring (e.g. holter monitor) and consultation with a cardiologist. A cardiologist should be consulted if QTcF intervals do not return to less than the criteria listed above after 8 hours of monitoring (or sooner, at the discretion of the investigator).

In some cases, it may be appropriate to repeat abnormal ECGs to rule out improper lead placement as contributing to the ECG abnormality. It is important that leads be placed in the same positions each time in order to achieve precise ECG recordings. If a machine-read QTc value is prolonged, as defined above, repeat measurements may not be necessary if a qualified medical provider's interpretation determines that the QTcF values are in the acceptable range.

ECG values of potential clinical concern are listed in [Appendix 7](#).

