10.7. Appendix 7: ECG Findings of Potential Clinical Concern

ECG Findings That May Qualify as AEs

• Marked sinus bradycardia (rate <40 bpm) lasting minutes.• New PR interval prolongation >280 msec.• New prolongation of QTcF to >480 msec (absolute) or by \geq60 msec from baseline.• New-onset atrial flutter or fibrillation, with controlled ventricular response rate: ie, rate <120 bpm.• New-onset type I second-degree (Wenckebach) AV block of >30 seconds' duration.• Frequent PVCs, triplets, or short intervals (<30 seconds) of consecutive ventricular complexes.
ECG Findings That May Qualify as SAEs

• QTcF prolongation >500 msec.• New ST-T changes suggestive of myocardial ischemia.• New-onset left bundle branch block (QRS >120 msec).• New-onset right bundle branch block (QRS >120 msec).• Symptomatic bradycardia.• Asystole:
• In awake, symptom-free participants in sinus rhythm, with documented periods of asystole \geq3.0 seconds or any escape rate <40 bpm, or with an escape rhythm that is below the AV node.• In awake, symptom-free participants with atrial fibrillation and bradycardia with 1 or more pauses of at least 5 seconds or longer.• Atrial flutter or fibrillation, with rapid ventricular response rate: rapid = rate >120 bpm.• Sustained supraventricular tachycardia (rate >120 bpm) ("sustained" = short duration with relevant symptoms or lasting >1 minute).• Ventricular rhythms >30 seconds' duration, including idioventricular rhythm (heart rate <40 bpm), accelerated idioventricular rhythm (HR >40 bpm to <100 bpm), and

monomorphic/polymorphic ventricular tachycardia (HR >100 bpm (such as torsades de pointes)).

- Type II second-degree (Mobitz II) AV block.
- Complete (third-degree) heart block.

ECG Findings That Qualify as SAEs

- Change in pattern suggestive of new myocardial infarction.
- Sustained ventricular tachyarrhythmias (>30 seconds' duration).
- Second- or third-degree AV block requiring pacemaker placement.
- Asystolic pauses requiring pacemaker placement.
- Atrial flutter or fibrillation with rapid ventricular response requiring cardioversion.
- Ventricular fibrillation/flutter.
- At the discretion of the investigator, any arrhythmia classified as an adverse experience.

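### Section 8.2.3 triggers its 500 msec rule on uncorrected QT but confirms and releases on QTc, and leaves unclear whether hourly ECGs depend on confirmation

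*Protocol*

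**What the plan says.** Protocol Section 8.2.3 sets two triggers for extra ECG monitoring. Condition (a) is a postdose QTcF that has risen at least 60 msec from predose and exceeds 450 msec. Condition (b), and what follows either trigger, reads "an absolute QT value is ≥ 500 msec for any scheduled ECG. If either of these conditions occurs, then 2 additional ECGs", taken about 2 to 4 minutes apart to confirm the finding. Hourly ECGs come next, on the condition "If the QTc values from these repeated ECGs remain above the threshold value", and continue until QTc from 2 successive ECGs is below the triggering threshold.

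A new paragraph then opens with the same words and gives the hourly instruction alone: "If either of these conditions occurs, then a single ECG measurement must be repeated at least hourly until QTc values from 2 successive ECGs" are below that threshold. It mentions no confirmatory pair.

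Escalation to continuous monitoring and a cardiologist again states (b) on absolute QT of at least 500 msec, "for any scheduled ECG for greater than 4 hours (or sooner, at the discretion of the investigator"). The last rule changes metric: "A cardiologist should be consulted if QTcF intervals do not return to less than the criteria listed above after 8 hours of monitoring". The section also allows a waiver: "If a machine-read QTc value is prolonged, as defined above, repeat measurements may not be necessary" where a qualified medical provider finds QTcF acceptable.

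Appendix 7 (Section 10.7) uses QTcF throughout. "QTcF prolongation >500 msec" may qualify as an SAE, and "New prolongation of QTcF to >480 msec (absolute") may qualify as an AE.

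**The concern.** Two things need correcting.

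**Metric.** Condition (b) starts on one quantity and is confirmed and released on another, against the same 500 msec figure. QT and QTc agree only at 60 bpm. Away from that rate, a participant can trigger the rule and be released by the first repeats with nothing having changed. A participant whose corrected interval exceeds 500 msec may never trigger it.

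**Sequence.** One paragraph makes hourly ECGs conditional on confirmation, and the next does not. Nothing says which governs. The first paragraph also gives no rule for a split pair, with one confirmatory ECG above threshold and one below.

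At stake is whether a safety procedure can be carried out the same way by everyone who reads it. Section 8 calls adherence essential and bars waivers, so the instruction should be unambiguous.

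**Working it through.** **Inputs from the documents**
- Section 8.2.3: trigger (a), QTcF rise of at least 60 msec and QTcF above 450; trigger (b), QT of at least 500; confirmation and release on QTc; 8-hour rule on QTcF.
- Section 8.2.3 also lists QT and QTc as separate machine measurements.
- Section 5.2, exclusion 11: a baseline uncorrected QT above 450 is converted by Fridericia, and the QTcF is used for decisions. QTcF above 450 excludes, judged on a 3-ECG average once it is exceeded.
- Section 1.3: the Day 1 ECG is predose; the only routine postdose ECG is at discharge (about 144 h), or at early termination.

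**Assumptions.** QTc in the confirmation and release sentences means QTcF, since the section names no method there. Heart rates are illustrative.

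**Formula.** QTcF = QT / (60/HR)^(1/3).

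**Step 1: QT of exactly 500 msec, which meets (b).** At 50 bpm, (60/50)^(1/3) = 1.0627 and 500 / 1.0627 = 470.5.

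| Heart rate (bpm) | QTcF when QT = 500 | QT when QTcF = 500 |
|---|---|---|
| 45 | 454.3 | 550.3 |
| 50 | 470.5 | 531.3 |
| 55 | 485.7 | 514.7 |
| 60 | 500.0 | 500.0 |
| 65 | 513.5 | 486.8 |

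**Step 2: below 60 bpm.** At 50 bpm, any QT from 500 to 531 fires (b) with QTcF from 471 to 499.7. If rate and QT do not change, both confirmatory ECGs are below 500 on QTcF, so the trigger is unconfirmed and the release condition is already met. This does not cover every slow-rate case: QT 510 at 59 bpm is QTcF 507.2, which stays above threshold.

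**Step 3: above 60 bpm.** Take baseline QTcF 445 (eligible under Section 5.2) and postdose QTcF 504 at 65 bpm.
- Rise: 504 − 445 = 59, below 60, so (a) is not met.
- QT: 504 × (60/65)^(1/3) = 504 × 0.9737 = 490.7, below 500, so (b) is not met.

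No repeat is mandatory, although the reading is above the Appendix 7 line for a possible SAE. In whole milliseconds, a QTcF above 500 can miss (a) only if baseline exceeds 501 − 60 = 441.

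**Step 4: the two paragraphs compared.**

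| Confirmatory pair | First paragraph | Second paragraph |
|---|---|---|
| Both above threshold | Hourly until 2 successive below | Same |
| Both below threshold | No hourly ECGs | Hourly ECGs ordered, unless the pair counts as the 2 successive ECGs below threshold |
| One above, one below | Not stated | Hourly until 2 successive below |

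The paragraphs agree in the first row. The second row depends on interpretation. In the third row only the second paragraph gives an answer, so deleting it without replacement would open a gap.

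**The case against.** **The intended metric can be inferred.** The word absolute in (b) may only contrast with the change from baseline in (a). Section 5.2, the 8-hour rule, the waiver and Appendix 7 all decide on QTcF. That is a fair reading of intent, and it makes a one-word slip the likely cause. The literal text is still QT, twice, in a section that names QT and QTc separately. If QTcF was meant, the edit states it; if QT was meant, the confirmation and release rules are wrong.

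**Other provisions catch the cases.** Appendix 7 would flag a QTcF of 504, Section 8.2.3 allows abnormal ECGs to be repeated, and Section 1.3 allows unplanned visits. This stands: what is lost above 60 bpm is the mandatory sequence, not all attention to the reading. The case is also narrow, needing a baseline above 441 and a rise under 60. The waiver does not cure the mismatch: it is worded for a prolonged QTc, leaves (b) on QT, and cannot help a reading that never triggers.

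**Stronger readings that the documents do not support.** A reader might infer that a site cannot follow both paragraphs. It can: taking the pair and then hourly ECGs satisfies both, and so does counting two below-threshold confirmatory ECGs as release, because at least hourly is a minimum frequency. A reader might also infer that release on QTc collides with escalation on QT after 4 hours. That is weak: once repeats are released, no further ECG is required, so nothing would document 4 hours of prolonged QT.

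**Conclusion.** The point holds as a minor wording error in a safety decision rule. Condition (b) is triggered and escalated on uncorrected QT but confirmed and released on QTc. The second paragraph is an ambiguous near-duplicate, not a rival order: it leaves open whether hourly ECGs depend on confirmation.

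The numerical discrepancy is moderate at ordinary resting rates. At QT 500, QTcF is 29 msec lower at 50 bpm (500 − 471) and 14 msec higher at 65 bpm (514 − 500). The practical reach is small, with one routine postdose ECG per participant in about 6 healthy men after a single dose. ECG data are only listed under SAP Section 8.3.7, and no mass balance, metabolite or PK result depends on this rule.

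The conclusion on the text rests on a literal reading of QT in (b). The examples rest on Fridericia correction and the illustrative heart rates. The documents give no heart-rate distribution, so how often either case would arise cannot be estimated.

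**What to change.** In Section 8.2.3:
1. State (b) as an absolute QTcF of 500 msec or more, in both the trigger and the escalation sentence.
2. Judge confirmation and release on QTcF.
3. Merge the two paragraphs into one rule: take 2 confirmatory ECGs 2 to 4 minutes apart; stop if neither still meets the criterion, (a) or (b), that triggered them; otherwise, including a split pair, repeat at least hourly until 2 successive ECGs no longer meet it.

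The change is to protocol wording only. It has two costs. Below 60 bpm, a long uncorrected QT with QTcF under 500 no longer forces a repeat unless (a) is met; at 50 bpm this is QT 500 to 531. For example, QT 512 at 50 bpm is QTcF 482; with baseline 430 the rise is 52, so (a) is not met and only Appendix 7 review for QTcF above 480 remains. Hourly ECGs are also clearly not required after an unconfirmed trigger, which the second paragraph could be read to require.

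If the sponsor wants to keep the uncorrected-QT trigger, (b) could read QT or QTcF of 500 msec or more. That loses no trigger, but confirmation and release must then be judged on whichever metric fired.
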